6.3. Treatment Assignment

All enrolled subjects will be randomized initially to Cohorts 1, 2, 3 and 4 such that upon reaching 12 subjects total for all 4 cohorts, each cohort will contain 3 subjects. The experience of these 12 subjects has guided the further conduct of the study. Adverse events, safety labs and the rate of infusion reactions in individual cohorts will dictate the continuance of a specific cohort. After the completion of at least one treatment cycle the subject experience will be evaluated before enrollment is opened to all cohorts. The future enrollment will be randomized between all open cohorts.

At this time Cohorts 1-10 are closed to enrollment. Randomization into the remaining open cohorts will continue until the cohorts are closed due to enrollment reaching 6-20 subjects per cohort or due to the stopping rules for individual cohorts. Cohorts that have closed due to enrollment levels may be re-opened to increase the enrollment to the maximum total number of subjects permitted.

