6.3.1. Stopping Rules in an Individual Subject or in a Cohort

For this clinical trial a treatment period is defined as period of time from the beginning of dosing of the first study drug on a given dosing day (ie, Either saline placebo or SEL-110 during Part A of the study and SEL-037 during Part B of the study) to the beginning of the next scheduled dose of study drug, and has a typical duration of 28 days.

For Part C (Cohorts 13, 15, and 17), a treatment period is defined as the period of time from the beginning of dosing of SEL-212 to the beginning of the next scheduled dose of study drug.

Individual

For subjects in Cohorts 1 and 2, any subject who has a weekly serum uric acid value ≥ 6 mg/dl or $>50\%$ of their baseline (where baseline value refers to the pre-dose serum uric acid level from visit 4, Day 0, treatment period 1) at Day 21 of their current treatment cycle will not be eligible for the next dosing of SEL-037. The subject will be followed for 30 days post the last dose of study drug at which time they will have an End of Study assessment and their participation in the study will be terminated.

In Cohorts 3-8, 10-13, 15, and 17 only subjects whose ambient blood samples indicate a serum uric acid (sUA) value less than or equal to 1.0 mg/dL at any of the Day 21 visits will be eligible for the next dosing of SEL-212 (or SEL-037). All other subjects will be followed for 30 ± 2 days post the last dose of study drug at which time all of the End of Study assessments will be completed and their participation in the study will be terminated.

Cohort

If 5 subjects in any of Cohorts 1-5 or 7, or if 10 subjects in any of Cohorts 6, 8, 10, 11, or 12 have met the requirements for individual stopping of their participation in the trial as described above or have been stopped based on Section 6.4 then that cohort will no longer have any additional subjects enrolled in it. Those subjects who have been enrolled will continue until they fulfill the requirements

Study: SEL-212/201 Version: 7.1	Effective Date March 19, 2018
------------------------------------	----------------------------------

for individual stopping or complete the clinical trial treatment periods. If they continue to meet the requirements for continued participation they may continue in Part B of the study.

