In Part C, if 10 subjects in either of Cohorts 13, 15, or 17 have met the requirements for individual stopping of their participation in the trial as described above or have been stopped based on Section 6.4 then the cohort will no longer have any additional subjects enrolled in it. Those subjects who have been enrolled will continue until they fulfill the requirements for individual stopping or complete the clinical trial treatment periods. If they continue to meet the requirements for continued participation they may continue in the clinical trial.

The medical monitor, Investigator, IRB, or regulatory agency may also stop additional dosing or dose escalation based on any condition that warrants termination such as the discovery of an unexpected, serious or unacceptable risk to subjects or an unacceptable incidence of an expected event (e.g., unacceptable incidence or severity of infusion reactions) which suggests additional dosing is not warranted.

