6.4. Criteria for Study Termination

The study will be terminated when the subjects have completed follow-up assessments as per Section 1.1 or the medical monitor, Sponsor, Investigators, safety committee, IRB or regulatory agencies have determined there is an unacceptable risk to subjects or additional dosing or procedures are not warranted or necessary.

The study may be terminated at a particular investigational site under the following conditions:

- The Investigator fails to enroll subjects at an acceptable rate;
- The Investigator fails to comply with pertinent regulations;
- There is insufficient adherence to the protocol;
- Knowingly false information is submitted to the IRB, Sponsor or designee, or regulatory authorities;

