7.4.3. Enrolled Subject Withdrawal and Discontinuations

7.4.3.1. Withdrawal Procedures

Early terminations are when an enrolled subject withdraws consent or the Investigator terminates a subject. The reason for withdrawal will be evaluated and recorded in the case report form (CRF) and source documents. Subjects that withdraw may be replaced (see Replacement of Subjects, Section 7.4.4).

Subjects may withdraw consent at any time. A documented effort must be made to determine why a subject withdraws consent, fails to return for the necessary visits, or is dropped from the study. All subjects that withdraw early upon termination should have the Early Termination visit assessments completed (i.e., End of Study assessments), if the assessments pose no risk to the subject and the subject allows such assessments.

The Investigator should consult with the Sponsor/medical monitor prior to withdrawing any subject. Since this is a multiple dose safety study, once dosed, subjects generally should not be terminated by the Investigator and should be followed through 30 days after last dose of study drug unless the subject withdraws consent or is lost to follow-up. In situations where continued participation in certain aspects of the study pose a risk to the subject, with consultation with the medical monitor, the Investigator should discontinue those procedures that pose a risk and should continue to collect data and conduct those assessments that do not put the subject at risk through 30 days after last study drug (e.g., End of Study). Subjects with compliance issues or major deviations that effect data quality will also continue to be followed through 30 days after last study drug collecting as much data on the subject as possible, unless otherwise indicated by the Sponsor.

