7.4.4. Replacement of Subjects

An excessive rate of withdrawal of subjects and missing data within a cohort can have a negative impact on this study given the small cohort size. Subjects may be replaced at the discretion of the Sponsor based on a review of withdrawal rates within a cohort, the impact of missing or unusable data, out of window blood draws and protocol deviations or other unanticipated events. No additional subjects will be replaced or dosed if the reason for withdrawal was the fulfilment of the stopping rules for individuals or cohorts.

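### The cohort-closing count in Protocol 6.3.1 cites Section 6.4, which has no criterion for stopping one subject; read literally, a safety stop with controlled urate is not counted

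*Protocol*

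**What the plan says.** The count in Protocol 6.3.1 has two limbs. The first is the individual stopping rule set out above it. In Cohorts 3-8, 10-13, 15 and 17 a Day-21 sUA at or below 1.0 mg/dL is required for the next dose. In Cohorts 1 and 2 a subject stops at 6 mg/dL or more, or above 50% of baseline. Neither rule mentions adverse events.

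The second limb is the cross-reference: "or have been stopped based on Section 6.4 then that cohort will no longer have any additional subjects enrolled in it". The threshold is 5 subjects in Cohorts 1-5 and 7, and 10 in Cohorts 6, 8, 10, 11 and 12. Part C (Cohorts 13, 15 and 17, threshold 10) repeats it: "or have been stopped based on Section 6.4 then the cohort will no longer have any additional subjects enrolled in it". The synopsis carries the same rules.

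Section 6.4 is headed as criteria for terminating the study. Its first sentence says when the study ends: when follow-up is complete, or when the named parties "have determined there is an unacceptable risk to subjects or additional dosing or procedures are not warranted or necessary". Its second part concerns sites: "The study may be terminated at a particular investigational site under the following conditions".

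Safety discontinuation of one subject is handled in 7.4.3.1: "with consultation with the medical monitor, the Investigator should discontinue those procedures that pose a risk". The count does not cite that section. Section 7.4.4 then says: "No additional subjects will be replaced or dosed if the reason for withdrawal was the fulfilment of the stopping rules for individuals or cohorts".

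**The concern.** The second limb sends the reader to a section that cannot answer the question it raises, namely which individual subjects have been stopped. Taken at its word, the limb either has no effect (if the study-level clause is met, closing one cohort is moot) or picks up the wrong people (subjects at a site closed for slow recruitment or poor compliance, which says nothing about the dose).

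The subject most likely intended, one taken off drug for safety, is left to interpretation. If urate is still controlled on Day 21, that subject is not counted. Because 7.4.4 bars replacement only when a stopping rule was fulfilled, the same subject may also be replaced at the sponsor's discretion. The rule is in use: Cohorts 11 and 12 are enrolling up to 20 each, Part C up to 40 in total, and cohorts closed because of enrolment levels may be re-opened.

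**Working it through.** The plan states no operating characteristic for this rule, so there is no figure to reproduce. The check is mainly on the text.

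**Who is counted, SEL-212 cohorts**

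| Why the subject is off drug | Day-21 sUA | Limb 1 (urate) | Limb 2 (6.4, literal) |
|---|---|---|---|
| Urate failure | above 1.0 | yes | not needed |
| Safety stop | above 1.0 | yes | not needed |
| Safety stop | no value | arguably yes, under the 6.3.1 sentence covering everyone not at or below 1.0 | not needed |
| Safety stop | at or below 1.0 | no | no |
| Site closed | at or below 1.0 | no | unclear |

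The gap is the fourth row. An infusion reaction will often fall outside it. If a first-period reaction during SEL-110 prevents SEL-037 from being given, urate is not lowered (Protocol 4.3.2.2; SAP 5.4), so the subject fails Day 21 and counts. Antibody-driven reactions will often come with lost urate control (Protocol 4.3.2.3 and 4.5). What remains is, for example, a rapamycin-type event such as stomatitis while urate is still controlled. Stomatitis occurred as SAEs in Phase 1 at 0.5 mg/kg SEL-110, above the doses used here.

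**Illustration 1: chance of reaching 10.** The documents give no rates, so all inputs except the threshold are assumed. Let N subjects have known outcomes, k of them uncounted safety stops, and let each of the others stop on urate with chance u.
- As written: P[Bin(N−k, u) ≥ 10]
- With safety stops counted: P[Bin(N−k, u) ≥ 10−k]

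| N, k | u=30% | u=40% | u=50% | u=60% |
|---|---|---|---|---|
| 19, 1 | 0.021 vs 0.060 | 0.135 vs 0.263 | 0.407 vs 0.593 | 0.737 vs 0.865 |
| 19, 2 | 0.013 vs 0.105 | 0.092 vs 0.359 | 0.315 vs 0.685 | 0.641 vs 0.908 |
| 15, 1 | 0.002 vs 0.008 | 0.018 vs 0.058 | 0.090 vs 0.212 | 0.279 vs 0.486 |
| 12, 1 (Part C) | 0.000 vs 0.001 | 0.001 vs 0.006 | 0.006 vs 0.033 | 0.030 vs 0.119 |

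The Part C row assumes 40 subjects over three cohorts, about 13 each. Every row is conditional on k uncounted subjects already existing. At N=19 in a 20-subject cohort, only one place is left to block.

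**Illustration 2: extra subjects enrolled.** This is closer to the consequence. Let each subject be an uncounted safety stop with chance a, each of the others stop on urate with chance u, and L be the number of most recent enrolees whose outcomes are not yet known. Replacement is ignored.
- Expected enrolment in a 20-subject cohort = Σ over n=0 to 19 of P[Bin(max(0, n−L), p) ≤ 9]
- As written p = (1−a)u; with safety stops counted p = (1−a)u + a

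The difference, in subjects, is:

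| L, a | u=30% | u=40% | u=50% | u=60% |
|---|---|---|---|---|
| 0, 2% | 0.04 | 0.16 | 0.33 | 0.42 |
| 0, 5% | 0.12 | 0.42 | 0.82 | 1.04 |
| 5, 5% | 0.01 | 0.03 | 0.12 | 0.29 |

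**The case against.** The strongest reply is that the literal reading empties the clause. Section 6.4 names the medical monitor, sponsor, investigators and safety committee, and speaks of unacceptable risk and of further dosing not being warranted. Applied to one subject, that is a safety stop, and a sensible reader would take it so. This was probably the intent, and that sites would diverge in practice is conjecture. The sentence is nevertheless about the study, and a rule that decides enrolment should not rest on inferred intent.

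The second reply is that this count is not the operative safety rule, and that stands. Reaching 5 or 10 ends only new enrolment; enrolled subjects continue while they qualify. Section 6.3 says: "Adverse events, safety labs and the rate of infusion reactions in individual cohorts will dictate the continuance of a specific cohort". The last paragraph of 6.3.1 adds that the medical monitor, investigator, IRB or regulator "may also stop additional dosing or dose escalation based on any condition that warrants termination". Section 6.3.2 has the safety committee review a cohort after related or possibly related SAEs in two subjects. A reader might infer from the faulty reference that the protocol lets safety stops accumulate without any cohort-level check. These three provisions show otherwise. They do not repair the count: the first two carry no number, and the third triggers review rather than closure.

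The third reply is that the probabilities in illustration 1 look larger than the consequence. That also stands, for the reasons given beside that table.

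**Conclusion.** The defect holds on the text, and it is minor. All three statements of the count rely on a section with no subject-level criterion, so a safety stop whose Day-21 urate still meets the continuation criterion is literally uncounted. The same gap exists in Cohorts 1 and 2 with their own urate limits. It matters mainly for Cohorts 11 and 12 and any re-opened cohort; in Part C, with about 13 subjects per cohort, a count of 10 is seldom reached under the assumed rates.

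The text conclusion depends on no assumed rate. The size does: between almost none and about one extra subject per 20-subject cohort, for an uncounted-stop rate of 2% or 5%, u of 30% to 60%, and outcomes known at once; at most about 0.3 at the 5% rate if outcomes lag by five enrolments. A reader might take illustration 1 as an estimate of how often closure is missed. The documents do not support that, because they give neither a urate-stop rate nor an adverse-event discontinuation rate.

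**What to change.** In 6.3.1 (Parts A/B and Part C) and in the synopsis, replace the Section 6.4 phrase with: *have been permanently discontinued from study drug because of an adverse event, including an infusion reaction, assessed as related or possibly related to study drug*. The causality test matches the one in 6.3.2. Add a sentence that exits for consent, compliance, site closure or an unrelated event do not count. In 7.4.4, state that subjects counted this way are treated as having fulfilled a stopping rule and are not replaced. Leave the thresholds of 5 and 10 unchanged.

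Identify these subjects from adverse-event causality (11.2.2.2), the item on whether the event caused the patient to discontinue the study (11.2.2), and the dosing records. That item alone is not enough, because it concerns leaving the study and 7.4.3.1 allows follow-up to continue after drug is stopped. The drug-withdrawn code in 11.2.2.5 is not enough either, because it means only that an infusion was terminated.

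The cost is one phrase in three places and two added sentences in an amendment, plus a short derivation from existing records. The downside is that a cohort may close to enrolment slightly earlier.

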6.3.2. Safety committee

Safety data will be monitored on an ongoing basis by the Investigators and medical monitor. If two or more subjects in a single cohort experience SAEs that are assessed as related or possibly related to study drug, then the safety committee will review all relevant safety information for all subjects in that cohort. The data will include the accumulated data through the time of the scheduled meeting. At minimum, this committee will include the Investigators, or their representatives, who have had subjects dosed at their site in the cohort of interest, the medical monitor and a sponsor representative.

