6.2. Number of Subjects

Number of patients (planned): In Part A and Part B, approximately 100 subjects will be divided into 11 dosing cohorts, each consisting of 6-20 subjects. Cohorts 1-10 are closed to enrollment but are permitted to be re-opened to increase the enrollment to the maximum total number of subjects permitted. Cohorts 11 and 12 will continue enrolling up to 20 subjects per cohort. Cohort 1 will receive SEL-037 (pegsiticase alone, 0.2 mg/kg), Cohort 2 will receive SEL-037 (pegsiticase alone, 0.4 mg/kg), Cohort 3 will receive SEL-212 (with 0.05 mg/kg of SEL-110 + 0.2 mg/kg pegsiticase), Cohort 4 will receive SEL-212 (with 0.05 mg/kg of SEL-110 + 0.4 mg/kg pegsiticase), Cohort 5 will receive SEL-212 (with 0.08 mg/kg of SEL-110 + 0.2 mg/kg pegsiticase), Cohort 6 will receive SEL-212 (with 0.08 mg/kg of SEL-110 + 0.4 mg/kg pegsiticase), Cohort 7 will receive SEL-212 (with 0.1 mg/kg of SEL-110 + 0.2 mg/kg pegsiticase), Cohort 8 will receive SEL-212 (with 0.1 mg/kg of SEL-110 + 0.4 mg/kg pegsiticase), Cohort 10 will receive SEL-212 (with 0.125 mg/kg of SEL-110 + 0.4 mg/kg pegsiticase), Cohort 11 will receive SEL-212 (with 0.15 mg/kg of SEL-110 + 0.2 mg/kg pegsiticase), and Cohort 12 will receive SEL-212 (with 0.15 mg/kg of SEL-110 + 0.4 mg/kg pegsiticase). Note that Cohort 9 is intentionally omitted from this protocol in order to maintain the cohort numbering convention of associating even numbered cohorts with the 0.4 mg/kg SEL-037 dose.

In Part C, up to 40 patients naïve to SEL-212 will be enrolled. Patients enrolled in Cohort 13 will receive SEL-212 (0.15 mg/kg SEL-110 + 0.2 mg/kg SEL-037). Patients enrolled in Cohort 15 will receive an initial induction dose of SEL-212 (0.15 mg/kg SEL-110 + 0.2 mg/kg SEL-037) and, then, four subsequent doses of SEL-212 (0.10 mg/kg SEL-110 + 0.2 mg/kg SEL-037). Patients enrolled in Cohort 17 will receive SEL-212 (0.10 mg/kg SEL-110 + 0.2 mg/kg SEL-037). (Note: Cohorts 14 and 16 are intentionally omitted from this protocol in order to maintain the cohort numbering convention of associating odd numbered cohorts with the 0.2 mg/kg SEL-037 dose.)

Subjects who withdraw early or have significant protocol deviations or compliance issues may be replaced at the discretion of the Sponsor to assure completion of the objectives of the clinical study and to maintain the integrity of the data set.

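### The safety committee trigger counts affected subjects one cohort at a time, although some cohorts share the same SEL-110 + SEL-037 dose for part of the course

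*Protocol*

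**What the plan says.** Protocol Section 6.3.2 first states the routine arrangement: "Safety data will be monitored on an ongoing basis by the Investigators and medical monitor". It then gives the trigger, "If two or more subjects in a single cohort experience SAEs that are assessed as related or possibly related to study drug", and its consequence: "then the safety committee will review all relevant safety information for all subjects in that cohort". Both the count and the scope of the review are tied to one cohort. No section of the protocol or SAP pools cohorts for this purpose.

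Protocol Section 6.2 assigns the doses. For Cohort 11: "Cohort 11 will receive SEL-212 (with 0.15 mg/kg of SEL-110 + 0.2 mg/kg pegsiticase". For Cohort 13: "Patients enrolled in Cohort 13 will receive SEL-212 (0.15 mg/kg SEL-110 + 0.2 mg/kg SEL-037". For Cohort 15: "Patients enrolled in Cohort 15 will receive an initial induction dose of SEL-212 (0.15 mg/kg SEL-110 + 0.2 mg/kg SEL-037", followed by four doses with SEL-110 at 0.10 mg/kg. Cohorts 7 and 17 both receive 0.1 + 0.2 mg/kg. Under Section 6.1, Cohorts 7 and 11 switch to SEL-037 alone in Periods 4-5, while the Part C cohorts stay on the combination.

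Two other provisions bear on the point. Section 6.3 says that "the rate of infusion reactions in individual cohorts will dictate the continuance of a specific cohort". Section 6.3.1 adds a discretionary power: "The medical monitor, Investigator, IRB, or regulatory agency may also stop additional dosing or dose escalation based on any condition that warrants termination".

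**The concern.** A count of two within a cohort is a sensible backstop while each cohort is a distinct dose. Part C broke that link. One affected subject in Cohort 11 and one in Cohort 13, both during Periods 1-3, are two affected subjects with the same dosing history, yet neither cohort reaches two. A third affected subject, in Cohort 15 after its first dose, would still not oblige the committee to meet. If the trigger did fire in Cohort 13, the mandated review need not look at Cohort 11.

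The gap matters in practice because Cohort 11 is still enrolling, up to 20 subjects, when Part C opens, and 0.15 mg/kg is the highest SEL-110 dose in the study. Cohort 7 is closed but may be re-opened, and its existing events are relevant to Cohort 17 either way. The primary objective is safety and tolerability, and a review that comes late, or is never required, weakens the one numeric safeguard the sponsor chose to write down.

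The SAP already uses the overlap elsewhere. Its Sections 8.5 and 8.6 provide for combining Part A with Part C Periods 1-3 in the PK analyses.

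**Working it through.** The documents give no operating characteristic for the trigger, so there is no stated figure to reproduce.

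**Where doses coincide (Protocol Sections 6.1 and 6.2)**

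- 0.15 + 0.2 mg/kg: Cohorts 11 and 13 in Periods 1-3, and Cohort 15 in Period 1.
- 0.1 + 0.2 mg/kg: Cohorts 7 and 17 in Periods 1-3. Cohort 15 receives this dose in Periods 2-5, but after a different first dose.

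The most subjects who can be affected without a trigger is one per cohort. That is two for Cohorts 11 and 13 (or 7 and 17), and three when Cohort 15 is added.

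**Inputs for the illustration**

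- Cohort 11: n = 20, its stated maximum.
- Cohorts 13 and 15: n = 13 each. This is assumed, from up to 40 subjects over three Part C cohorts; the split is not stated.
- Risk that a subject has a related SAE: not stated, so 2% to 10% is assumed. Phase I gives 2/31 = 6.5% (Section 4.3.2.3), but both subjects received 0.1 + 0.4 mg/kg as a single dose.
- Subjects are independent and have equal risk.

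**Exactly two subjects affected: chance that they fall in different cohorts**

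- Formula: 1 − Σ C(n,2) / C(N,2).
- Cohorts 11 and 13: 1 − (190 + 78)/528 = 0.49.
- Cohorts 11, 13 and 15: 1 − (190 + 78 + 78)/1035 = 0.67.

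**Chance that the trigger fires, at 5% risk**

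- P(X ≤ 1) = 0.95^n + n × 0.05 × 0.95^(n−1). This gives 0.7358 for n = 20, 0.8646 for n = 13, 0.5036 for n = 33 and 0.3232 for n = 46.
- As written, Cohorts 11, 13 and 15: 1 − 0.7358 × 0.8646² = 0.45.
- All events in the three cohorts counted together: 1 − 0.3232 = 0.68.
- Cohorts 11 and 13 only: 1 − 0.7358 × 0.8646 = 0.36 as written, and 1 − 0.5036 = 0.50 counted together.

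The same formulas at other risks:

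| Risk | 11+13+15 as written | 11+13+15 together | 11+13 as written | 11+13 together |
|---|---|---|---|---|
| 2% | 0.11 | 0.24 | 0.09 | 0.14 |
| 5% | 0.45 | 0.68 | 0.36 | 0.50 |
| 6.5% (2/31) | 0.60 | 0.81 | 0.50 | 0.64 |
| 10% | 0.85 | 0.95 | 0.76 | 0.86 |

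**Allowing for when events occur.** Counting every event together is right only while dosing is shared. I simulated 400,000 trials at 5% risk. The pooled count added Period 1 events across Cohorts 11, 13 and 15, and Period 1-3 events across Cohorts 11 and 13; the within-cohort counts were kept.

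- Risk even over five doses: 0.50.
- Risk even over the first three doses: 0.58.
- All risk at dose 1: 0.68.

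The rule as written gives 0.45 in each case.

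**The case against.** The strongest reply is that oversight does not depend on this count. The study is open label, so a cohort label hides no dose from anyone. SAEs must be reported within 24 hours (Section 11.3.2). The Investigators and medical monitor watch safety continuously, Section 6.3.1 lets several parties stop dosing, and Section 6.4 names the safety committee among those who may find the risk unacceptable, with no count required. All of this stands. It means that what is missing is a mandated committee review, not review altogether. It does not remove the point, because none of these provisions obliges the committee to meet on same-dose events.

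Four stronger readings are tempting, and the documents do not support them.

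- A reader might infer that the cohorts have identical regimens. No two cohorts share a planned five-dose course. The courses of 11 and 13, or of 7 and 17, become the same only if the late-toxicology fallback in Section 4.5.1 is used.
- A reader might take 0.68 as the gain from pooling. That needs all the risk at dose 1, because Cohort 15 shares the dose only then.
- A reader might conclude that splitting by label mainly determines whether the trigger fires. In the three-cohort table the assumed risk moves the as-written probability from 0.11 to 0.85, whereas the split moves it by 0.10 to 0.23.
- A reader might add one event per cohort over all 14 cohorts. That total mixes different doses, SEL-037 alone and closed cohorts. The rule also counts subjects, so several SAEs in one subject are one.

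On infusion reactions, Section 6.3.1 already names their unacceptable incidence or severity as a ground for stopping, so the statement in Section 6.3 is not without a route. What remains unclear is how those sections and the committee trigger fit together.

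**Conclusion.** The point holds in a limited form. The trigger and the review it mandates are per cohort, while doses overlap across cohorts for Periods 1-3 (11 with 13, 7 with 17) and at the first dose (15 with 11 and 13). Two or three subjects with related SAEs at one dose can therefore occur without an obligatory committee review.

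The structural finding rests on the text alone. Its size is illustrative. Under the assumed sizes and a 5% risk, counting same-dose subjects together raises the chance of a mandated review by about 0.05 if risk is even over five doses (0.50 − 0.45) and by at most 0.23 if all risk falls at dose 1 (0.68 − 0.45). Early stopping under the uric acid rule would weight exposure towards the shared periods, but by how much is not known. The change is worth making because it restores the intended meaning of the count at very little cost.

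**What to change.** In Protocol Section 6.3.2, keep the existing committee and the existing count of two subjects. State that the count applies within a cohort and also across cohorts whose subjects have received the same SEL-110 + SEL-037 dosing up to the time of the event, and that the review covers all subjects with that dosing. List the groups for clarity: Cohorts 11, 13 and 15 at the first dose, Cohorts 11 and 13 through the third, and Cohorts 7 and 17 through the third. What the committee decides is left to it.

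The cost is a sentence or two in the protocol, possibly one or two extra meetings, and a slightly higher chance of a review that finds nothing.

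Separately, the sponsor should reconcile the Section 6.3 statement on infusion-reaction rates with Sections 6.3.1 and 6.3.2, saying who assesses those rates and how they reach the committee. No grade or rate threshold is proposed here.
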